6.7.2. Laboratory Data

Laboratory data will be listed and summarized in accordance with the Pfizer reporting standards. Change from baseline analyses using the SAF-RA analysis set will describe the movement of laboratory assessments from Study Baseline to Week 12, randomization baseline and then again from Week 16 to the end of randomized treatment for all the three regimens. Similarly, change from baseline analyses using the SAF-RE analysis set will

describe the movement of laboratory assessments from Rescue Baseline to the end of the rescue period. Results from analyses of absolute values as well as of change from baseline will be displayed using both tabular and graphical formats.

6.7.3. Vital Signs, including Height and Weight

Vital signs will be summarized at all scheduled visits. Height and weight will be summarized at all visits where they are assessed.

6.7.4. Electrocardiogram

ECG parameters, if applicable, will be summarized at all assessment visits.

6.7.4.1. Physical Examination

Physical examinations will be summarized at all assessment visits.

6.7.5. Asthma Control Questionnaire (ACQ)

The questions on the ACQ are equally weighted and the ACQ score (or the response) for each subject is the mean of the 5 questions and therefore between 0 (totally controlled) and 6 (severely uncontrolled). Categorical summary of the responses to the individual questions will be summarized using methods in [Section 5.2.3](#).

7. INTERIM ANALYSES

This study uses an External Data Monitoring Committee (E-DMC). The E-DMC will be responsible for ongoing monitoring of the efficacy, safety and PKs of subjects in the study according to the charter. Any recommendations made by the E-DMC to alter the conduct of the study will be forwarded to Pfizer for final decision. Pfizer will forward such decisions, which may include summaries of aggregate analyses of endpoint events and of safety data that are not endpoints, to regulatory authorities, as appropriate. Composition of the E-DMC and processes under which the E-DMC operates will be documented in the E-DMC charter.

9. APPENDICES

Appendix 1. Summary of Clinical Efficacy Analyses

Clinical Efficacy Endpoints	Analysis Set	Baseline	Analysis Method	Missing Data Imputation	Primary Analysis for Primary Endpoint
Loss of Response	FAS-RA	Randomization Date	Time to Event	CAR	Yes
Loss of Response	PPAS	Randomization Date	Time to Event	CAR	No
Loss of Response	FAS-RA	Randomization Date	Time to Event	CNAR	No
Loss of Response based on the IGA score	FAS-RA	Randomization Date	Time to Event	CAR	
Loss of Response based on the IGA score	PPAS	Randomization Date	Time to Event	CAR	
Weeks 2, 4, 8 and 12 IGA Response	FAS-OL	Study	Normal approx.	NR	
Weeks 12, 16, 28, 40 and 52 IGA Response	FAS-RA	Study	CMH and Normal approx.	NR	
Rescue Weeks 2, 4, 8 and 12 IGA Response	FAS-RE	Study	Normal approx.	NR	
Weeks 12, 16, 28, 40 and 52 EASI-50 Response	FAS-RA	Study	CMH and Normal approx.	NR	
Weeks 2, 4, 8 and 12 EASI-75 Response	FAS-OL	Study	Normal approx.	NR	
Weeks 12, 16, 28, 40 and 52 EASI-75 Response	FAS-RA	Study	CMH and Normal approx.	NR	
Rescue Weeks 2, 4, 8 and 12 EASI-75 Response	FAS-RE	Study	Normal approx.	NR	
Weeks 12, 16, 28, 40 and 52 EASI-90 Response	FAS-RA	Study	CMH and Normal approx.	NR	
Weeks 2, 4, 8 and 12 NRS4 Severity Response	FAS-OL	Study	Normal approx.	NR	
Weeks 12, 16, 28, 40 and 52 NRS4 Severity Response	FAS-RA	Study	CMH and Normal approx.	NR	
Rescue Weeks 2, 4, 8 and 12 NRS4 Severity Response	FAS-RE	Study	Normal approx.	NR	
Weeks 12, 16, 28, 40 and 52 SCORAD50 Response	FAS-RA	Study	CMH and Normal approx.	NR	
Rescue Weeks 2, 4, 8 and 12 SCORAD50 Response	FAS-RE	Study	Normal approx.	NR	
Weeks 12, 16, 28, 40 and 52 SCORAD75 Response	FAS-RA	Study	CMH and Normal approx.	NR	
Rescue Weeks 2, 4, 8 and 12 SCORAD75 Response	FAS-RE	Study	Normal approx.	NR	
Weeks 12, 16, 28, 40 and 52 CFBL in Total EASI Score	FAS-RA	Randomization	MMRM	OD	
Rescue Weeks 2, 4, 8 and 12 PCFBL in Total EASI Score	FAS-RE	Rescue	MMRM	OD	
Weeks 12, 16, 28, 40 and 52 CFBL in Total SCORAD Score	FAS-RA	Randomization	MMRM	OD	
Rescue Weeks 2, 4, 8 and 12 PCFBL in Total SCORAD Score	FAS-RE	Rescue	MMRM	OD	
Weeks 12, 16, 28, 40 and 52 CFBL in NRS Score for Severity	FAS-RA	Randomization	MMRM	OD	
Rescue Weeks 2, 4, 8 and 12 CFBL in NRS Score for Severity	FAS-RE	Rescue	MMRM	OD	
Weeks 12, 16, 28, 40 and 52 CFBL in Percent BSA	FAS-RA	Randomization	MMRM	OD	
Rescue Weeks 2, 4, 8 and 12 PCFBL in Percent BSA	FAS-RE	Rescue	MMRM	OD	

CFBL=Change from baseline; PCFBL=Percent change from baseline; CMH=Cochran-Mantel-Haenszel; MMRM=Mixed-effect Model Repeated Measures; NR=Non-Responder; OD=Observed Data; CAR=Censoring at Random; CNAR=Censoring not at Random

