#### **Clinical Efficacy Assessments in Subjects Requiring Rescue Treatment:**

1. Response based on the IGA at the end of rescue therapy.
2. Response based on the EASI total score at the end of rescue therapy.
3. Response based on achieving  $\geq 4$  point improvement in the severity of pruritus Numerical Rating Scale (NRS) at the end of rescue therapy relative to the start of rescue therapy baseline value.
4. Percent change in percent Body Surface Area (BSA) at the end of rescue therapy relative to the start of rescue therapy baseline value.
5. Percent change in SCORAD subjective assessments of itch and sleep loss at the end of rescue therapy relative to the start of rescue therapy baseline value.
6. Response based on achieving a  $\geq 50\%$  and  $\geq 75\%$  improvement in SCORAD (SCORAD-50, SCORAD-75) at the end of rescue therapy relative to the start of rescue therapy baseline value.

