##### **4.1. Inclusion Criteria**

Subjects must meet all of the following inclusion criteria to be eligible for enrollment into the study:

1. Evidence of a personally signed and dated informed consent document indicating that the subject, or his/her legally acceptable representative/parent(s) or legal guardian if a minor, have been informed of all pertinent aspects of the study.
2. Male or female subjects of 12 years of age or older, at the time of informed consent and body weight  $\geq 40$  kg. Adolescent subjects below the legal age of majority (legal adulthood) in the subject's country will only be enrolled in this study if instructed by the sponsor and approved by the country's regulatory/health authority. If these approvals have not been granted, only subjects  $\geq$  the legal age of majority (legal adulthood) in the subject's country will be enrolled.
3. Meet all the following atopic dermatitis criteria:
  - Clinical diagnosis of chronic atopic dermatitis (also known as atopic eczema) for at least 1 year prior to Day 1 and has confirmed atopic dermatitis at the screening and baseline visits according to Hanifin and Rajka criteria of AD (see [Appendix 2](#)).
  - Documented recent history (within 6 months before the screening visit) of inadequate response to treatment with medicated topical therapy for AD for at least 4 weeks, or who have required systemic therapies for control of their disease.

NOTE: Medicated topical therapy is defined as a topical product that contains an active pharmaceutical ingredient indicated for the treatment of AD (irrespective of whether it is an over-the-counter [OTC] or prescription only product).

- Moderate to severe AD (affected BSA  $\geq 10\%$ , IGA  $\geq 3$ , EASI  $\geq 16$  and pruritus NRS severity  $\geq 4$  on the day of the baseline visit).
4. Willing and able to comply with scheduled visits, treatment plan, laboratory tests and other study procedures.
  5. Female subjects who are of child-bearing potential (which includes adolescents aged 12 years and older regardless of whether they have experienced menarche) must not be intending to become pregnant, currently pregnant, or lactating. The following conditions apply:
    - a. Female subjects of childbearing potential must have a confirmed negative pregnancy test prior to treatment with investigational product;

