### **9.2.4. Analysis of Secondary Endpoints**

In general, binary endpoints (such as EASI-50, EASI-90 or the proportion of subjects achieving  $\geq 4$  point improvement in severity of pruritus NRS measure) will be analyzed using the (Cochran-Mantel-Haenszel) test adjusted by randomization strata (age groups) and baseline disease severity. The difference between treatment groups in the proportion of subjects achieving a response along with its 95% confidence interval (using the normal approximation for the difference in binomial proportions) will be reported. If a subject withdraws from the study, then this subject will be counted as a non-responder for endpoints

after withdrawal. In addition, a subject in the FAS-RA subset who receives rescue treatment due to protocol-defined flare will be considered a non-responder.

For continuous endpoints, such as percent change from baseline in the EASI total score and BSA or change from baseline in SCORAD, PSAAD, DLQI/CDLQI, POEM, HADS, and change from baseline in the pruritus severity using the NRS measure, a mixed-effect model with repeated measures (MMRM) will be used. This model will include the factors (fixed effects) for treatment group, randomization strata (age groups), and baseline disease severity, visit, treatment-by-visit interaction, and relevant baseline value. Within the framework of MMRM, differences between groups will be tested using estimates from the MMRM model.

For all binary endpoints, missing data will be handled by considering subjects who withdraw or randomized subjects receiving rescue treatment as non-responders. No imputations will be made for continuous data and missing data will be considered to be MAR.

In general all secondary endpoints will be analysed for the FAS-RA subset. For the subjects requiring rescue therapy (FAS-RE subset), the response achieved at the end of the rescue period will be assessed in relation to the start of the rescue period. In addition to these two analysis sets, secondary endpoints will also be summarized for all subjects participating in the open-label run-in period (FAS-OL subset).

Hypotheses for all relevant secondary endpoints will be tested at the nominal 5% level of significance, without adjustments for multiple comparisons.

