4.1. Full Analysis Set (FAS)

The following groups of FAS will be defined for this study:

FAS-OL: This is the set of all subjects who received at least one dose of study treatment during the open label run-in phase. For all analyses, Study Baseline will be used (see [Section 3.4](#)).

FAS-RA: This is the set of all subjects who have been randomized at Week 12 and have received at least one dose of study treatment within the double-blind phase. By study design, this will be a subset of FAS-OL. Subjects are assigned to the randomized treatment group regardless of actual treatment received. All analyses will be reported by treatment

regimen/sequence (eg, OL 200 mg → DB 200 mg or OL 200 mg → DB 100 mg or OL 200 mg → DB Placebo). For analysis purposes, either the Study Baseline or the Randomization Baseline will be used, depending on the endpoint and/or the analysis (see [Sections 3.4 and 6](#)).

FAS-RE: This is the set of all subjects who have met the protocol definition of a flare (see [Section 2.2](#)) during the double-blind phase and have received at least one dose of rescue treatment. By study design, this will be a subset of FAS-RA. In general, for efficacy analyses, Rescue Baseline will be used (see [Section 3.4](#)).

In general, change from baseline analyses based on any of the above FAS groups will require at least one post-baseline observation recorded. Analyses for endpoints that are defined based on a threshold of change from baseline (eg, NRS4) will also require the baseline value to meet that threshold (eg, for NRS4, the baseline value needs to be ≥ 4).

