6.3. Secondary Endpoints (Efficacy)

6.3.1. Response Based on (IGA, EASI-50, EASI-75, EASI-90, EASI-100, NRS4 for Severity of Pruritus, SCORAD50 and SCORAD75, IGA + EASI-75)

	All Randomized Subjects	Randomized Subjects Requiring Rescue Treatment	Pre- Randomization Subjects
Summary	Proportion of subjects achieving a response at Weeks 12, 16, 28, 40 and 52	Proportion of subjects achieving a response at Rescue Weeks 2, 4, 8 and 12	Proportion of subjects achieving a response at Weeks 2, 4, 8 and 12
Population	FAS-RA	FAS-RE	FAS-OL
Baseline	Study (see Section 3.4)	Rescue (see Section 3.4)	Study (see Section 3.4)
Statistical Method	CMH and normal approximation as in Section 5.2.1 .	Normal approximation as in Section 5.2.1 .	Normal approximation as in Section 5.2.1 .
Missing Data	Missing values after dropout are defined as “non-response” (see Section 5.3.1)	Missing values after dropout are defined as “non-response” (see Section 5.3.1)	Missing values after dropout are defined as “non-response” (see Section 5.3.1)

6.3.2. Change from Baseline in (Total EASI Score, SCORAD (VAS) Pruritus and Sleep Sub-Scales, PP-NRS for Severity and Percent BSA)

	All Randomized Subjects	Randomized Subjects Requiring Rescue Treatment
Summary	Change from baseline at Weeks 12, 16, 28, 40 and 52	Percent change/Change from baseline at Rescue Weeks 2, 4, 8 and 12
Population	FAS-RA	FAS-RE
Baseline	Study (for Week 12); Randomization (for visits after Week 12) (see Section 3.4)	Rescue (see Section 3.4)
Statistical Method	MMRM as in Section 5.2.2	MMRM as in Section 5.2.2
Missing Data	Use observed data (see Section 5.3.2)	

Change from Study Baseline at Week 12 and its 95% CI will be estimated for each randomized treatment group using an MMRM analysis using data from Weeks 2, 4, 8 and 12. For PP-NRS, data will be included from Days 2 – 15, Weeks 4, 8 and 12.

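### SAP Appendix 1 lists Study Baseline for the five rescue-phase responder analyses, whereas SAP 6.3.1 and protocol 9.2.4 measure rescue response from the start of rescue

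*SAP*

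**What the plan says.** SAP 3.4 defines Study, Randomization and Rescue Baseline as three separate values, so the label in a table decides the analysis.

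- **SAP Appendix 1.** The FAS-RE responder rows cover IGA, EASI-75, NRS4 ("Rescue Weeks 2, 4, 8 and 12 NRS4 Severity Response"), SCORAD-50 and SCORAD-75. Each has Study in the Baseline column. The FAS-RE change rows in the same table, such as "Rescue Weeks 2, 4, 8 and 12 CFBL in NRS Score for Severity", have Rescue.
- **SAP 6.3.1.** The column for randomized subjects needing rescue covers those five endpoints at the same visits. Its baseline entry is "Rescue (see Section 3.4").
- **SAP 4.1, on FAS-RE.** "In general, for efficacy analyses, Rescue Baseline will be used".
- **Protocol 9.2.4, on FAS-RE.** "the response achieved at the end of the rescue period will be assessed in relation to the start of the rescue period".
- **Endpoint lists (Protocol Summary, protocol Table 1, SAP Table 2).** NRS4 and SCORAD-50/75 are assessed "at the end of rescue therapy relative to the start of rescue therapy baseline value". The IGA and EASI items name no baseline.

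**The concern.** Two tables in one SAP give different baselines for the same five analyses, and no text marks either as an exception or says which prevails. A programmer could follow either one, and either result could later be called pre-specified.

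Efficacy of rescue treatment is a stated secondary objective. Subjects enter rescue after a flare, with scores that usually differ from those at study entry. Improvement since study entry mixes whatever remains of the run-in and maintenance benefit with the effect of rescue; improvement since rescue entry does not. The choice of baseline changes who counts as a responder and, for NRS4, who is in the denominator.

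**Working it through.** **Baselines side by side**

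| Source | Endpoints | Visits | Baseline |
|---|---|---|---|
| SAP Appendix 1, FAS-RE responder rows | IGA, EASI-75, NRS4, SCORAD-50, SCORAD-75 | Rescue Weeks 2, 4, 8, 12 | Study (5 of 5) |
| SAP 6.3.1, FAS-RE column | those five and others | Rescue Weeks 2, 4, 8, 12 | Rescue |
| Protocol 9.2.4 | response in FAS-RE | end of rescue | start of rescue |
| Protocol Table 1, SAP Table 2 | NRS4, SCORAD-50/75 | end of rescue | start of rescue |
| Same lists | IGA, EASI | end of rescue | none named |
| SAP 4.1 | FAS-RE efficacy, in general | not specified | Rescue |

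For NRS4 and SCORAD-50/75, Appendix 1 conflicts with 6.3.1, with protocol 9.2.4 and with the endpoint definition itself. For IGA and EASI-75 it conflicts with 6.3.1 and 9.2.4, and departs from the general rule in 4.1. Protocol 9.2.4 speaks only of the end of rescue, so for Rescue Weeks 2, 4 and 8 the conflict rests on the SAP.

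**NRS4**

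Inputs: NRS severity is at least 4 "on the day of the baseline visit" (protocol 4.1). Flare uses only EASI and IGA (SAP 3.1), so NRS at rescue entry is unrestricted. For threshold endpoints SAP 4.1 "will also require the baseline value to meet that threshold".

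Let s be study-entry NRS (4 to 10) and e rescue-entry NRS (0 to 10), giving 7 × 11 = 77 pairs. Under Study Baseline, response is already met at rescue entry when s − e ≥ 4.

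- Count for s = 4, 5, …, 10: 1 + 2 + 3 + 4 + 5 + 6 + 7 = 28 pairs.
- Of these, e ≥ 4 in six: (8,4), (9,4), (9,5), (10,4), (10,5), (10,6).
- The other 28 − 6 = 22 have e of 0 to 3. Those subjects leave the NRS4 denominator under Rescue Baseline.

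**EASI-75**

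Let x0 be study-entry EASI and xR Week 12 EASI. The SAP 3.1 flare threshold is xR + 0.5 × |xR − x0| = 0.5 × (x0 + xR). With x0 = 40 and xR = 10 this gives 25, as in the SAP's example.

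- A randomized responder has 0 ≤ xR ≤ 0.25 × x0, so the threshold lies between 0.50 × x0 and 0.625 × x0.
- The Study Baseline cut is 0.25 × x0. From the threshold, the fall needed is 1 − 0.25/0.50 = 50% up to 1 − 0.25/0.625 = 60%. Under Rescue Baseline it is always 75%.
- Because rescue entry is at least 0.50 × x0, EASI-75 is never already met at rescue entry.

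In the SAP example (Study cut 0.25 × 40 = 10):

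| Rescue-entry EASI | Fall needed, Study | Fall needed, Rescue | Rescue cut |
|---|---|---|---|
| 25 | 60.0% | 75% | 6.25 |
| 30 | 66.7% | 75% | 7.5 |
| 35 | 71.4% | 75% | 8.75 |
| 40 | 75.0% | 75% | 10 |
| 48 | 79.2% | 75% | 12 |

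Study Baseline is the easier criterion below study-entry EASI, equal at it, and stricter above it.

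**IGA**

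Response is a score of 0 or 1 with a drop of at least 2 (SAP 3.3.1). From study entry at 3 or 4, both 0 and 1 qualify. From rescue entry at 2, only 0 qualifies; from 3 or 4, both do.

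**SCORAD**

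The cuts are 0.5 or 0.25 times whichever baseline is used. The documents set no SCORAD limit at study or rescue entry, so no comparable bound can be given.

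**The case against.** - **Mixed baselines can be deliberate.** In the randomized set (FAS-RA) the SAP uses Study Baseline for responders and Randomization Baseline for change after Week 12, in both 6.3 and Appendix 1. Every responder row in Appendix 1 says Study, which could be a convention. This stands as far as it goes: Rescue in the FAS-RE change rows does not by itself show that the responder rows are wrong. The case rests on 6.3.1 and the protocol.
- **IGA and EASI-75 may have been meant as recapture against study entry.** Their endpoint wording omits the start-of-rescue phrase, SAP 4.1 speaks only in general, and the SAP may modify the protocol. The support for these two rows is thinner. But 6.3.1 is specific, names both endpoints and says Rescue, and the freedom to modify the protocol does not explain the SAP contradicting itself.
- **Appendix 1 is only a summary.** Section 6 introduces it that way, and it omits several endpoints that 6.3.1 covers in this set. That lowers the practical risk, but no precedence rule is stated.
- **The NRS4 count is not a frequency.** This is correct. Low itch at rescue entry may be uncommon, because protocol 5.2 gives returning pruritus as a reason to contact the site, though flares are also assessed at scheduled visits.

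**Conclusion.** The contradiction is real, and Appendix 1 is the outlier. Following it would compute NRS4 and SCORAD responses that disagree with their own endpoint definitions, and IGA and EASI-75 responses that disagree with SAP 6.3.1 and protocol 9.2.4.

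The response definitions differ materially, but the reach is limited. SAP 5.2 and 6 make no treatment comparisons in FAS-RE, so only single-arm descriptive summaries are affected. It should be corrected but does not threaten the trial's main conclusions.

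The EASI and IGA figures assume that Rescue Baseline is the flare-visit value and that every randomized subject met EASI-75 at Week 12. The net direction of change in response rates cannot be stated, because it depends on rescue-entry scores the documents do not give.

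**What to change.** Before database lock and unblinding, change Study to Rescue in the five FAS-RE responder rows of SAP Appendix 1. Add one sentence stating that, for IGA, a subject entering rescue at 2 can respond only by reaching 0. If recapture of response against Study Baseline is of interest, report it as a separately labelled additional analysis.

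The cost is five table cells and a sentence, with no extra analysis unless the recapture summary is added. One downside should be accepted knowingly: the NRS4 denominator becomes subjects with rescue-entry NRS of at least 4, rather than all rescued subjects (all of whom had at least 4 at study entry), so it may be smaller.

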Appendix 2. Definition and Use of Visit Windows in Reporting

Visit windows will be used for efficacy variables, and for any safety lab data that display or summarize by study visit. For other endpoints (eg, ECG, vital signs), visit windows will be applied for summary statistics by study visits if required.

Visit Windows Applicable for Run-In and Blinded Phases

Visit Label	Target Day	Definition [Day window]
Screening		Days -28 to Day -1
Study Baseline	Day 1 (Day of first dose)	Last observation prior to and including day of first dose
Week 2	15	Days 2 to 22
Week 4	29	Days 23 to 43
Week 8	57	Days 44 to 71
Week 12	85	Days 72 to 99 but not beyond first randomized dosing date
Week 16	113	Days 100 to 155 but after first randomized date
Week 28	197	Days 156 to 239
Week 40	281	Days 240 to 323
Week 52	365	Days 324 to 379
Week 56	-	Days 380 to -

For the lab values, if the calculated study day for the labelled baseline visit is not study Day 1 but falls within 28 days before the start of the study dosing, then that data should be used for the baseline instead of leaving baseline missing.

For the other values, if the calculated study day for the labelled baseline visit is not study Day 1, but falls before the start of the study dosing, then that data should be used for the baseline instead of leaving baseline missing.

Visit Windows Applicable for Rescue Therapy Phase

Rescue Visit Label	Target Day*	Definition [Day window*]
Rescue Baseline	Day 1 (Day of first rescue dose)	Last dose of blinded treatment until Day 1
Rescue Week 2	15	Days 2 to 22
Rescue Week 4	29	Days 23 to 43
Rescue Week 8	57	Days 44 to 71
Rescue Week 12	85	Days 72 to 99
Rescue Week 16	-	Days 100 to -

- * Days are relative to Day 1 being the first day of rescue therapy.

If two or more visits fall into the same window, keep the one closest to the Target Day. If two visits are equaled distant from the Target Day in absolute value, the later visit should be used.

If there are more than one observations collected on the same day, the one with the latest time should be used.

Safety analysis may follow CaPS standards.

